12.4.2 Analysis of Secondary Endpoints

Our secondary outcome analyses will use ANOVA to test for group differences in change in performance on the remaining cognitive tasks (Multiple Object Tracking, Digit Span Backwards, Simple RT, Choice RT, Letter Number Switch) and group differences in the WHODAS 2.0, our secondary measure of daily functioning.

12.5 Interim Analysis

Interim analyses will be provided to Akili Interactive as requested.

12.6 Reporting and Exclusions

12.6.1 Evaluation of Toxicity

Not applicable.

12.6.2 Evaluation of Response

All subjects included in the study will be assessed for response to the intervention (if they have received the intervention).

13. Adverse Event Reporting Requirements

The research team is responsible for notifying the WCM IRB of all unexpected adverse events and serious adverse events. After faxing or e-mailing the Cornell IRB reporting forms to Cornell, the Research Assistant should follow-up with an e-mail or phone call to verify that the forms were received. Additionally, copies of these forms should be kept in the patient file as source documentation.

In addition to the WCM IRB, AEs, SAEs, death, protocol violations, non-compliance, suspensions and terminations will be reported to the Akili Interactive (as the industry funding partner). All reports must be made in writing to Akili. These reports should indicate that the monitoring entities (i.e., the PI and IRB) have been notified in accordance with the approved monitoring plan.

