For participants without access to technology that would allow them to consent electronically, the participant and researcher will review the consent form over the phone. A copy of the consent form will be mailed or emailed to the participant in advance so that it can be viewed by the participant during the phone call. They will return the signed consent form in a stamped, self-addressed envelope provided by the researcher. These participants will then be mailed a copy of their signed consent form for their records.

To screen prospective participants, we will conduct an initial screening via a secure HIPAA-compliant videoconferencing platform (Zoom). Participants will be queried for inclusion and exclusion criteria. Participants will be administered via Zoom the Oral Trail Making Test, Stroop Test, and the Frontal Systems Behavior Rating Scale (FrSBe). Participants will be eligible for enrollment if they score <1 standard deviation below their age-normed peers on at least one of these three screening tests.

Participants will be randomized into the intervention arm or a waitlist control arm, with an option for the control participants to receive the AKL-T01 intervention at the conclusion of the initial 6-week waitlist period.

All participants (intervention & waitlist control arm): Full assessment visits will take place pre-intervention (baseline) and post-intervention (week 6). During the 6-week intervention period, shorter intermediate assessment visits will take place at weeks 2 and 4. Participants in the waitlist control arm will continue any ongoing self- or provider-based cognitive intervention (or no intervention) during the initial 6-week waitlist period.

Participants in the intervention arm & participants in the control arm who decline the intervention: A full assessment session at will take place at week 10 (4 weeks post-intervention) for longitudinal follow-up.

Participants in the control arm who begin the intervention at the conclusion of the waitlist period: The week 6 assessment visit will also serve as the baseline for the beginning of the intervention. Intermediate assessment visits will take place at weeks 8 and 10, a full post-intervention assessment visit will take place at week 12, and a follow-up assessment visit will take place at week 16 (4 weeks post-intervention).

See Section 6.1 for the complete Schedule of Assessments.

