7.9 Duration of Therapy and Criteria for Removal from Study

In the absence of intervention delays due to adverse event(s), intervention may continue until one of the following criteria applies:

- Intercurrent illness that prevents further administration of the intervention,
- Unacceptable adverse event(s),
- Subject decides to withdraw from the study, or
- General or specific changes in the subject's condition render the subject unacceptable for further intervention in the judgment of the investigator.
- The investigators of this study may stop the study or remove participants from the study at any time should they judge that it is in the participants' best interest to do so or if they do not comply with the study plan.

For device/interventional studies -

Study Termination Guidelines: A subject's follow-up in the study will end after one of the following applies:

- Subject's voluntary withdrawal
- Subject lost to follow-up
- Completion of all scheduled study follow-up appointments

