8.2 Participant Discontinuation/Withdrawal from the Study

Participants are free to withdraw from participation in the study at any time upon request. An investigator may discontinue or withdraw a participant from the study for the following reasons:

- Significant study intervention non-compliance
- If any clinical adverse event (AE), laboratory abnormality, or other medical condition or situation occurs such that continued participation in the study would not be in the best interest of the participant.
- Participant lost to follow-up after several attempts to contact subject to schedule study visit.

The reason for participant discontinuation or withdrawal from the study will be recorded in the case report form (CRF). Subjects who sign the informed consent form and are randomized but do not receive the study intervention may be replaced. Subjects who sign the informed consent form, and are randomized and receive the study intervention, and subsequently withdraw, or are withdrawn or discontinued from the study, will not be replaced.

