12.1 Study Design/Endpoints

We will test the hypothesis that patients receiving the AKL-T01 intervention will have significantly enhanced improvement in cognition and daily functioning, relative to a waitlist control group.

- 1) Our primary cognitive measure will be change in performance on a Digit Symbol Matching Task from baseline (pre-intervention) to week 6 (post-intervention) in all participants randomized to the AKL-T01 intervention arm or the waitlist control arm.
- 2) Our primary daily functioning measure will be change in score on the NeuroQOL Cognitive Function scale from baseline (pre-intervention) to week 6 (post-intervention) in all participants randomized to the AKL-T01 intervention arm or the waitlist control arm.

We will use analysis of variance (ANOVA) to test for differences in 1) Digit Symbol Matching and 2) NeuroQOL change scores across the intervention and control arms.

A secondary outcome analyses will use ANOVA to test for group differences in change in performance on the remaining cognitive tasks (Multiple Object Tracking, Digit Span Backwards, Simple RT, Choice RT, Letter Number Switch) and group differences in the WHODAS 2.0, our secondary measure of daily functioning.

We will use the Holm-Bonferroni method to correct for multiple comparisons. An intent-to-treat approach will be used in for all of the analyses above, including outcomes in participants who did not complete the intervention.

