12.4 Analysis of Endpoints

12.4.1 Analysis of Primary Endpoints

Our primary cognitive measure will be change in performance on a Digit Symbol Matching Task from baseline (pre-intervention) to week 6 (post-intervention) in all participants randomized to the intervention or control arm. Our primary daily functioning measure will be change in score on the NeuroQOL Cognitive Function scale from baseline (pre-intervention) to week 6 (post-intervention) in all participants randomized to the intervention or control arm. We will use analysis of variance (ANOVA) to test for differences in Digit Symbol Matching and NeuroQOL change scores across the two arms.

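### Section 12.6.2 makes response assessment conditional on having received the intervention, which conflicts with the intent-to-treat analysis of all randomised participants in 12.1 and 12.4.1

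*Combined protocol and SAP*

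**What the plan says.** **Analysis population.** Section 12.4.1 defines the primary week-6 change comparison "in all participants randomized to the intervention or control arm", and 12.1 uses equivalent wording. Section 12.1 adds: "An intent-to-treat approach will be used in for all of the analyses above, including outcomes in participants who did not complete the intervention".

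**Response assessment.** Section 12.6.2 falls under 12.6, Reporting and Exclusions. It reads: "All subjects included in the study will be assessed for response to the intervention (if they have received the intervention" (the last clause is a parenthesis in the protocol).

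**What controls receive.** Section 3.1 says: "Participants in the waitlist control arm will continue any ongoing self- or provider-based cognitive intervention (or no intervention) during the initial 6-week waitlist period". They are offered AKL-T01 only after week 6, and 3.1 provides for "participants in the control arm who decline the intervention". Sections 3.1 and 6.1.2.1 schedule the full baseline and week-6 assessments in both arms.

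**Replacement.** Section 8.2 states: "Subjects who sign the informed consent form and are randomized but do not receive the study intervention may be replaced". It does not mention their place in the analysis.

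**Removal and discontinuation.** Section 8.2 lists "Significant study intervention non-compliance" among the reasons an investigator may withdraw someone from the study. Section 7.9 allows removal of participants "if they do not comply with the study plan". Section 8.1 says that stopping AKL-T01 is not the same as leaving the study, and that post-intervention assessments are to be collected when someone stops.

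**The concern.** The plan gives two answers to the question of who counts in the efficacy comparison. An analyst working from 12.1 and 12.4.1 keeps everyone randomised. An analyst who looks for the exclusion rule finds it under a heading that names exclusions, and may drop randomised people who never started AKL-T01.

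Such a rule would be one-sided. Starting AKL-T01 before week 6 is possible only in the AKL-T01 arm, so people who do not take up their allocation could be filtered out there while similar people stay in the waitlist arm. The two groups would then no longer be the groups that randomisation formed. In an unblinded trial, where people know their arm before deciding whether to begin, non-starting may well be related to prognosis or motivation.

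The non-compliance provisions raise a related problem. Removing someone from the study for not following the gameplay schedule can end the collection of the outcome data that an intent-to-treat analysis needs. During weeks 0 to 6, only the AKL-T01 arm has gameplay to comply with.

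**Working it through.** The plan gives no figure on this point, so the check is mainly a comparison of texts.

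**Step 1: the two rules side by side.**

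| Section | Who is included | Condition on receipt |
|---|---|---|
| 12.1 | All randomised, both arms, intent-to-treat, non-completers included | None |
| 12.4.1 | All randomised, both arms | None |
| 12.6.2 | All subjects in the study | Must have received the intervention |

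The first two agree and the third differs. No section says which prevails. The illustration in 12.1 covers people who did not complete the intervention and does not name people who never began. The all-randomised wording does cover them.

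**Step 2: whom the condition could affect at week 6.** Sections 3.1 and 6.1.2.1 assess both arms at week 6, and section 10 measures the effect against the waitlist over weeks 0 to 6. Controls are thus part of the comparison without having received AKL-T01. What remains for the condition to select on is non-starting in the AKL-T01 arm.

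**Step 3: whether such people can exist.** Section 6.1.1 randomises at the end of the screening visit. Section 6.1.2.1 places gameplay training at the later week-0 visit. Section 7.11 says participants know their arm. Someone can therefore be allocated to AKL-T01, know it, and never begin. The documents do not say how many are expected.

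**Step 4: replacement under 8.2.** A replaced person has been randomised, so 12.1 and 12.4.1 already include that person. Section 8.2 does not say so. This is a missing link and not a second contradiction.

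**Step 5: non-compliance.** Section 8.1 concerns stopping AKL-T01; 8.2 and 7.9 concern leaving the study. They address different events, and the power to remove is optional. However, one participant who stops playing could be kept and assessed under 8.1, or removed under 8.2 or 7.9, and nothing says how the provisions fit together.

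**Step 6: what determines the size of a bias, if the condition were applied.** Let f be the share of the AKL-T01 arm excluded, and D the amount, in SD units of change, by which the excluded would have done worse than the rest of their arm. Let m be the mean of those retained.

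- Mean of the arm as randomised: (1 − f) × m + f × (m − D) = m − f × D.
- Exclusion therefore raises the arm mean by f × D.

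Neither f nor D is in the documents. Assumed values only show the mechanism: f = 5% with D = 0.25 gives 0.05 × 0.25 = 0.0125 SD, and f = 20% with D = 0.8 gives 0.20 × 0.8 = 0.16 SD. If the excluded would have done better than the rest, D is negative and the shift reverses. These values do not estimate anything for this trial.

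**Step 7: the cost of keeping everyone.** If non-starters gain nothing, the expected effect is multiplied by (1 − f). From the d of about 0.4 in section 12.2:

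- f = 5%: 0.4 × 0.95 = 0.38
- f = 10%: 0.4 × 0.90 = 0.36
- f = 20%: 0.4 × 0.80 = 0.32

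I do not convert these to power. The 88% in 12.2 was simulated for a mixed model whose variance components are not given, whereas 12.4.1 names an ANOVA of change scores.

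**The case against.** The strongest defence is that 12.6.2 does not define an analysis set. It says who is assessed for response to the intervention, and on one natural reading only recipients can respond to it. The population for the primary analysis is set explicitly in 12.1 and again in 12.4.1. The text around 12.6.2 also shows template residue: toxicity evaluation and progression-free survival are marked not applicable, and unfilled placeholders remain in 14.1.2. This carries weight. It makes actual exclusion less likely and is the reason to treat the point as a correction. It does not remove the conflict: the sentence sits under a heading on exclusions, carries a condition that 12.1 and 12.4.1 lack, and is not limited to a descriptive summary of recipients.

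Three stronger readings are tempting, and the documents do not support them.

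- **That 12.6.2 excludes the whole waitlist arm.** Taken in isolation, it could. But 3.1 and 6.1.2.1 assess controls at week 6, and every statement of the primary comparison is against the waitlist.
- **That replacement under 8.2 removes people from the analysis.** Section 8.2 does not say this, and 12.1 and 12.4.1 include everyone randomised.
- **That the anticipated 20% loss measures how many non-starters would be dropped.** It is not specific to one arm. The Protocol Summary and 12.2 both give 50 randomised per arm, and 125 × 0.80 = 100 fits a loss before randomisation. The exact timing is a separate clarification and has no bearing on 12.6.2.

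It can also be said that 8.1 and 8.2 do not clash, because one is about stopping the intervention and the other about leaving the study. That is right as far as it goes. What stands is that they are not reconciled.

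**Conclusion.** The point holds as a contradiction in the text. Section 12.6.2 attaches a receipt condition that the intent-to-treat population in 12.1 and 12.4.1 does not have. Applied to the week-6 comparison, it could in practice act only on AKL-T01 participants who never start, and the comparison would then no longer be as randomised. Confidence is high on the wording.

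There is no basis for saying that exclusion will happen, since the plan's main statements point towards keeping everyone. The direction and size of any bias depend on how many would be dropped and how they would have fared, and the documents give neither.

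The non-compliance provisions in 8.2 and 7.9 are unreconciled with 8.1. They bear on the same analysis because they govern whether week-6 data continue to be sought.

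**What to change.** 1. In 12.6.2, delete the parenthesis. State that the primary week-6 analysis includes everyone randomised, in the assigned arm, whether or not AKL-T01 was started, and that this includes anyone replaced under 8.2. If a summary in recipients is wanted, label it as descriptive and supplementary.
2. Reconcile 8.2 and 7.9 with 8.1, and all three with the intent-to-treat analysis, so that a reader can tell what happens to outcome collection when someone does not comply. The content of any withdrawal rule is for the study team; no rule is proposed here.

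**Cost.** These are wording changes only, with no change to visits, devices or training. Non-starters who stay in the analysis dilute the effect by the factor (1 − f), a cost that the intent-to-treat commitment in 12.1 already carries. Seeking week-6 assessments from them takes some staff effort, and anyone who refuses assessment will still have missing data.

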13.1 Adverse Event Definition

Adverse event is defined as any untoward medical occurrence associated with the use of an intervention in humans, whether or not considered intervention-related.

13.1.1 Investigational Agent or Device Risks (Expected Adverse Events)

We do not anticipate significant risks for our behavioral intervention beyond boredom, frustration, fatigue, and/or headaches.

13.1.2 Adverse Event Characteristics and Related Attributions

All AEs must have their relationship to study intervention assessed by the clinician who examines and evaluates the participant based on temporal relationship and his/her clinical judgment. The degree of certainty about causality will be graded using the categories below. In a clinical trial, the study device must always be suspect.

- **Definitely Related** – There is clear evidence to suggest a causal relationship, and other possible contributing factors can be ruled out. The clinical event, including an abnormal laboratory test result, occurs in a plausible time relationship to study intervention administration and cannot be explained by concurrent disease or other drugs or chemicals.
- **Probably Related** – There is evidence to suggest a causal relationship, and the influence of other factors is unlikely. The clinical event, including an abnormal laboratory test result, occurs within a reasonable time after administration of the study intervention, is unlikely to be attributed to concurrent disease or other

drugs or chemicals.

- **Potentially Related** – There is some evidence to suggest a causal relationship (e.g., the event occurred within a reasonable time after administration of the trial medication). However, other factors may have contributed to the event (e.g., the participant's clinical condition, other concomitant events). Although an AE may rate only as "possibly related" soon after discovery, it can be flagged as requiring more information and later be upgraded to "probably related" or "definitely related", as appropriate.
- **Unlikely to be Related** – A clinical event, including an abnormal laboratory test result, whose temporal relationship to study intervention administration makes a causal relationship improbable (e.g., the event did not occur within a reasonable time after administration of the study intervention) and in which other drugs or chemicals or underlying disease provides plausible explanations (e.g., the participant's clinical condition, other concomitant treatments).
- **Not Related** – The AE is completely independent of study intervention administration, and/or evidence exists that the event is definitely related to another etiology. There must be an alternative, definitive etiology documented by the clinician.

13.1.3 Recording of Adverse Events

All adverse events will be recorded on a subject specific AE log. The AE log will be maintained by the research staff and kept in the subject's research chart.

13.1.4 Reporting of AE to WCM IRB

All AEs occurring on this study will be reported to the IRB according to the IRB policy, which can be accessed via the following link:
http://researchintegrity.weill.cornell.edu/forms_and_policies/forms/Immediate_Reportin
Policy.pdf.

13.1.5 Reporting Events to Participants

Events leading to substantive changes in the consent form or procedures will be communicated to the current participants enrolled in the study.

13.1.6 Events of Special Interest

Not applicable.

13.1.7 Reporting of Pregnancy

Not applicable.

13.2 Definition of SAE

Serious adverse event or serious suspected adverse reaction. An AE or suspected adverse reaction is considered "serious" if, in the view of either the investigator or sponsor, it results in any of the following outcomes: death, a life-threatening adverse

event, inpatient hospitalization or prolongation of existing hospitalization, a persistent or significant incapacity or substantial disruption of the ability to conduct normal life functions, or a congenital anomaly/birth defect. Important medical events that may not result in death, be life-threatening, or require hospitalization may be considered serious when, based upon appropriate medical judgment, they may jeopardize the participant and may require medical or surgical intervention to prevent one of the outcomes listed in this definition. Examples of such an event would include a seizure or suicide attempt requiring inpatient hospitalization.

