Suicidal ideation may be identified by the PHQ-9. Identification of suicidal ideation will trigger a suicide risk assessment following an established protocol and algorithm developed by investigators in the Department of Psychiatry (see attached form). The suicide risk assessment will be completed under the supervision of a licensed clinician or by the licensed clinician themselves. Depending on the level of risk, study staff may provide referrals for further care, which may include outpatient or inpatient treatment according to clinical indication. Involuntary admission may become necessary in patients at acute and imminent risk for harming themselves. In the unlikely event that a licensed clinician is not available for immediate clinical evaluation of a subject reporting suicidal intent or plan, the research staff member will contact emergency medical services.

The suicide risk assessment classifies subjects who endorse suicidal ideation as having Mild Risk, Intermediate Risk, or High Risk. For subjects classified as having Mild or Intermediate Risk, referrals for outpatient mental health services will be provided and study staff will discuss a plan of action should the subject's frequency or intensity of ideation increase (call 911, go to ER). If the subject is classified as having High Risk with imminent danger of self-harm, then the study staff member will contact emergency medical services.

Risk assessment and safety monitoring will be conducted under the supervision of study staff who are licensed clinical psychologists

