13.2.1 Reporting of SAE to IRB

All SAEs occurring on this study will be reported to the IRB according to the IRB policy, which can be accessed via the following link:
http://researchintegrity.weill.cornell.edu/forms_and_policies/forms/Immediate_Report_Policy.pdf.

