13.2.3 Reporting of SAE to Akili Interactive

Institution will send Akili Interactive copies of any and all serious adverse event reports filed with the IRB, as well as copies of any correspondence with the IRB, regarding any and all serious adverse events, irrespective of association with the AKL-T01 intervention in the course of the Clinical Trial, within 5 business days of such report or correspondence being sent to the IRB. Copies should be sent via secure file transfer directly to [name] in the Clinical Research and Operations Department at Akili Interactive.

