13.4 Time Period and Frequency for Event Assessment and Follow Up

The occurrence of an adverse event (AE) or serious adverse event (SAE) may come to the attention of study personnel during study visits and interviews of a study participant presenting for medical care, or upon review by a study monitor.

All AEs including local and systemic reactions not meeting the criteria for SAEs will be captured on the appropriate case report form (CRF). Information to be collected includes event description, time of onset, clinician's assessment of severity, relationship to study product (assessed only by those with the training and authority to make a diagnosis), and time of resolution/stabilization of the event. All AEs occurring while on study must be

documented appropriately regardless of relationship. All AEs will be followed to adequate resolution.

Any medical condition that is present at the time that the participant is screened will be considered as baseline and not reported as an AE. However, if the study participant's condition deteriorates at any time during the study, it will be recorded as an AE.

Changes in the severity of an AE will be documented to allow an assessment of the duration of the event at each level of severity to be performed. AEs characterized as intermittent require documentation of onset and duration of each episode.

The study research assistant will record all reportable events with start dates occurring any time after informed consent is obtained until 7 (for non-serious AEs) or 30 days (for SAEs) after the last day of study participation. At each study visit, the investigator will inquire about the occurrence of AE/SAEs since the last visit. Events will be followed for outcome information until resolution or stabilization.

14. Unanticipated Problems Involving Risks to Subjects or Others

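### In Section 13.2, an admitted suicide attempt is used as an example of an important medical event that may not need admission; the mismatch could steer a non-admitted attempt away from the SAE label

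*Combined protocol and SAP*

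**What the plan says.** Section 13.2 builds the definition of a serious event in three steps.

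- It lists outcomes that each make an event serious. One of them is "inpatient hospitalization or prolongation of existing hospitalization".
- It then adds a judgment-based category: "Important medical events that may not result in death, be life-threatening, or require hospitalization may be considered serious when, based upon appropriate medical judgment", the event may put the participant in jeopardy and may need treatment to avert a listed outcome.
- It closes with the illustration: "Examples of such an event would include a seizure or suicide attempt requiring inpatient hospitalization".

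Several rules depend on the label.

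- Section 13.2.1: "All SAEs occurring on this study will be reported to the IRB according to the IRB policy".
- Section 13.2.3: the funding partner receives "copies of any and all serious adverse event reports filed with the IRB" within 5 business days of their going to the IRB.
- Section 13.4: events are recorded from consent "until 7 (for non-serious AEs) or 30 days (for SAEs) after the last day of study participation".

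Section 13.1.6 names no events of special interest, so no separate rule covers suicide attempts or seizures.

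The protocol expects to meet suicidality. Section 2.4.3 states: "Suicidal ideation may be identified by the PHQ-9", and sets out a risk assessment that follows. Table 1 in Section 6.1 schedules that scale weekly from week 0 to week 6. Section 4.3 excludes people with a recent attempt, with current suicide risk, or with a history of seizures.

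**The concern.** The added category exists to catch grave events that the listed outcomes miss, in particular those managed without admission. Its use is discretionary, and the example sentence is the only concrete guidance on how to use that discretion. That sentence describes an event which the admission criterion has already caught. A member of staff classifying a suicide attempt that was treated in an emergency department and discharged might conclude from it that admission is what makes an attempt serious.

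Visits are remote, so staff will often classify from a second-hand account and the written definition. What is at stake is how a rare but grave event is classified, how quickly it reaches the IRB and the funding partner as an SAE, and whether it is recorded at all if it begins late. No efficacy endpoint is involved.

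**Working it through.** No sample size, power or alpha figure is involved. The check sets the clauses side by side and then follows what the label decides.

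**1. Does the example fit its category?**

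- Suicide attempt with admission: meets the admission criterion in the first list. It is serious without the added category and so does not illustrate it. This holds on either reading of the grammar.
- Seizure: if the admission qualifier covers both nouns, the same failure applies. If it covers only the suicide attempt, the seizure example is sound. The sentence does not settle which.
- Suicide attempt without admission: this is the case the category is for, and no example covers it.

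**2. What changes with the label for a non-admitted attempt?**

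| Rule | Labelled serious | Labelled non-serious |
|---|---|---|
| Recorded while on study | Yes (13.4) | Yes (13.4) |
| Recorded, days 1 to 7 after last participation | Yes (13.4) | Yes (13.4) |
| Recorded, days 8 to 30 after last participation | Yes (13.4) | No (13.4) |
| IRB | SAE route (13.2.1) | AE route under IRB policy (13.1.4); also as an unexpected AE (13, opening) |
| Funding partner | Copy within 5 business days of the IRB report (13.2.3) | Written AE report, no time limit stated (13, opening) |

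The unexpected-AE route applies because Section 13.1.1 lists only boredom, frustration, fatigue and headaches as anticipated.

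**3. Size of the recording gap** (inputs from Section 13.4 and the participant durations in Section 1)

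- Gap: 30 − 7 = 23 days, that is, days 8 to 30 after the last day of participation.
- Share of the post-participation window: 23/30 = 77%.
- Share of the whole recording period, about 10 weeks of participation: 23/(70 + 30) = 23/100 = 23%.
- Share of the whole recording period, 16 weeks (waitlist participants who take up the intervention): 23/(112 + 30) = 23/142 = 16%.

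The last two shares leave out the short interval between consent and week 0, which would lower them slightly.

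**4. Number of events.** The documents give no rate. Assuming 0 to 2 such events among the 100 participants in the target sample, only those starting in the 23-day gap would go unrecorded. The others would be recorded under the wrong label.

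**The case against.** The strongest reply is that the operative rule is intact and only its illustration is clumsy. The example sentence does not claim to be exhaustive. The clause before it describes an attempt treated in an emergency department quite directly. A life-threatening or incapacitating attempt is serious under the first list whether or not the person is admitted. All of this stands, so misfiling is made easier but is not required.

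A reader might infer that Section 13.2 counts an attempt as serious only if the person is admitted. The text contains no such restriction. A reader might also infer that a non-admitted attempt would go unreported. Sections 13 and 13.1.4 do not support that, since AEs still go to the IRB and the funding partner. The IRB policy is linked but not reproduced, so how it would treat such an event cannot be checked.

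The 77% is easily over-read, because it describes only the month after participation ends. Section 13.4 places the AE inquiry at study visits and none is scheduled in that month, so detection then would be incidental under either label. Nor does the suicide-risk response depend on the SAE label: Section 2.4.3 triggers it from reported ideation. Section 15 has no stopping rules and Section 12.6.1 plans no toxicity evaluation, so a miscounted SAE would alter no planned analysis or stopping decision.

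One part of the reply does not stand. It could be said that the example refers to serious events in general and is merely redundant. But the sentence follows directly on the important-medical-event clause and points back to it, so that reading is strained. Even a redundant example gives staff the wrong cue.

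**Conclusion.** The point holds as a defect in the wording of a safety definition. The suicide-attempt example in Section 13.2 does not fit the category it illustrates; the seizure example fails on one of two readings. The likely effect is a pull towards filing a non-admitted attempt as non-serious.

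The consequence is limited to three losses: the SAE-specific IRB route, the 5-business-day copy to the funding partner, and recording of an event that starts in the 23 days from day 8 to day 30 after last participation. This rests on two assumptions: that staff follow the example rather than the general clause, and that the unseen IRB policy does not itself correct the label. The documents do not support a claim that such events escape recording or reporting altogether, or that the efficacy comparison is affected. It is worth correcting because the text is operative, the event is grave and the change is small.

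**What to change.** Reconcile the example sentence in Section 13.2 with the category it illustrates. Either delete the closing qualifier about inpatient admission, or replace it with wording that says the event did not result in admission. Either change also removes the ambiguity over the seizure. Admitted cases remain serious under the existing criterion, and the category remains a matter of medical judgment.

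The cost is one phrase in an amendment and possibly a few more SAE reports. Nothing changes in treatment, visits, sample size or analysis.
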